	reduce simulation crisis medical error, randomized
	controlled clinical trial.
Recruitment Country	Colombia
Problem Studied	Medical error: omission of management steps in medical
	crises
Interventions	Intervention: training in non-technical skills and checklists
	Control: standard training with checklists
Inclusion and exclusion criteria	Inclusion: over 18 years.
	Final semester student of medicine at the University of
	Antioquia .
	Have passed the theoretical knowledge exam for handling
	crisis events with a score of 100%.
	On-site availability on training days
	Exclusion: having received training in a specific crisis
	resource management course. Refusing to participate
Type of study	Intervention

Table 1. WHO data record

	Superiority
Recruitment Start Date	Pending
Target sample size	56 participants
Study status	Elaboration of protocol
Primary outcome	Proportion of omissions of treatment steps per group.
Secondary outcomes	Crisis resolution time
	Time in detection and discrimination of the crisis
	Overall score of non-technical skills
	Discriminated score between dimensions of non-technical
	skills
	Student satisfaction
	Incidence of inadequate crisis management

3. Table 2. Protocol Version:

Version	Date	Modifications	
one	November 03, 2020		[name]

4. Financing: simulation center of the Faculty of Medicine, University of Antioquia and Authors.

5. Table 3. Research roles

Name	Assignment	Contributions		
[name] Principal investigator P		Preparation of protocol, collection		
		of patients, statistical analysis,		
		dissemination of results.		
[name]	Director of research	Protocol review.		
[name]	Co-investigator	Protocol review, patient collection.		

II. Introduction

6a. Background

Medical Error

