Medical error defined as an "unintentional act of omission or commission that does not result in the intended result, lack of planning, use of improper plan, or deviation from the plan of care that may or may not harm a patient" (one) it is a big public health problem. For 2013, it was estimated that medical error was the third leading cause of death in the United States. (2); and in Latin America the preventable adverse event and the injury secondary to medical error(3), has a prevalence of 10.5% (95% CI 9.91 to 11.04) of health care (4). A 2008 prospective multicenter cohort in Colombia described a cumulative incidence of 4.6% (95% CI 4.1 to 5.1) for preventable adverse events, with underreporting estimated by the authors of 20 to 40% (5), with similar incidents described in intensive care units(6)(7).

Medical error has been described in several contexts: skipping treatment steps in critical situations(8)medication error(9), diagnostic error(10), among others. Depending on the context, the encoding of such errors can include more than 400 types(eleven). Dovey et al. Propose a taxonomy of medical error in the following way: administrative failures; research failures, understood as the clinical and paraclinical search for a medical pathology; treatment failures; communication errors; failure in treatment decision; and diagnostic error(12).

However, from a cognitive point of view, medical error can be classified into two categories: slip, as that incorrect execution of a correct sequence of action; and error, such as the correct execution of an incorrect action sequence, each category in turn can be directed to treatment or diagnosis(13).

The omission of treatment steps in medical crises, that is, medical error in cardiac arrest or those code situations, is of special relevance given the severity of the context and the risk of mortality or serious adverse events, and due to the high incidence reported for this context, which is between 26 and 50%(8); with similar incidents for trained and training personnel(14).

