Table 4. Previous studies on non-technical skills or medical error.

Khoo EM and	Educational	Conventional	Diagnostic and	Decrease of medical	Clinical trial
Cols.(28)	package of	management	treatment	error 54.0% (Cl 49.9-	
	methods and	before	errors	58.0) to 36.6% (CI 30.2-	
	processes.	intervention		43.1)	
Starmer and Cols. (29)	Handoff training program focused on organizational culture and communication	Conventional management before intervention	Medical error and adverse event in a pediatric hospital	Reduction of incidence of medical error 24.5 vs 18.8 per 100 admissions P <0.001	Study Before and after
Wetmore et al.(30)	Use of anesthesia reinduction checklist	Simulation training without a checklist	Performance measured as skipping preparation steps	Improvement of 7.8 points out of 22 possible.	Simulated controlled clinical trial
Duclos and Cols. (31)	Crisis resource management course plus checklists	Checklists	Serious adverse events 30 days after surgery	8.8 to 5.5% (OR 0.57, 95% CI 0.48 to 0.68 versus 7.9 to 5.4% in control (OR 0.64, 0.50 to 0.81 ROR 0.67 to 1.21.	Controlled clinical trial
Doumouras and Cols.(32)	Non-technical skills training	Out of control	Crisis resolution time	Each point on the ANTS scale decreased the crisis resolution time by 53 seconds	Prospective cohort
Arriaga and Cols. (33)	Training with checklists	Conventional training	Errors in omitting treatment steps in crisis	Absolute risk reduction: 17% Relative risk of 0.28. IC0.18 to 0.42; P <0.001	Simulated controlled clinical trial

HNT: Non-technical skills, MRC: resource management in crisis. ANTS: Non-technical Skills Scale for Anesthesiologists.

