The problems with the studies carried out up to the moment of carrying out this protocol, in relation to medical error and non-technical skills, are varied. In the pilot study by Müller et al.(27), in which no sample size was calculated, a training day in resource management in CRM crisis was compared, a course that includes some dimensions of non-technical skills: leadership, assertive communication, situational awareness versus conventional medical management training in two scenarios in simulation; hemorrhagic shock and simulation non-intubation non-oxygenation situation; In both groups, performance measured with a checklist of treatment actions and non-technical skills measured with the Non-Technical Skills Scale for ANTS anesthesiologists was improved; without differences between both arms. However, no inference can be made from the population since this study has not been completed so far.

In the Khoo and Collaborators essay(28)An educational intervention was conducted to fill gaps in medical knowledge and aid in decision-making with decision algorithms in outpatient institutions, that is, only one dimension of the HNT, in primary care institutions. The results are not applicable to medical crises since it was carried out in a different context and also the way of measuring the outcome, review of medical records, is aimed at detecting an adverse event, that is, the potential damage derived from the care of health and not medical error.

In the study by Khan et al.(3. 4), only two specific dimensions of non-technical skills are included: assertive communication and teamwork; it was not possible to determine an overall reduction in medical error but a reduction in the risk of medical error with potential harm, a relative risk of 0.69 (95% CI 0.53 to 0.91) and an absolute risk reduction of 2% (95 CI). % 1 to 4).

The most important study on the reduction of medical error in crisis is that of Arriaga and Collaborators.(33) in which the use of checklists reduced the omission of simulation treatment steps with an absolute risk reduction of 17 and relative risk of 0.28 (95% CI). 0.18 to 0.42). These checklists impact one dimension of the HNT: resource management.

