Finally, as it is an educational strategy, the population that a priori benefits the most from these interventions is the personnel in training. In the case of the Faculty of Medicine of the University of Antioquia, the training of non-technical skills is not included in the micro curriculum of critical patient care, therefore, the results of the present study could be used to define modification or confirmation of the micro curriculum for critical patient care in the last semester of medicine.

6b. Comparison justification.

Until now, the use of checklists is the intervention that has the most empirical support in reducing medical error due to omission of steps in surgery (38). Arriaga et al. Found that the use of checklists reduces simulation crisis medical error with an absolute risk reduction of 17% and relative risk of 0.28. IC0.18 to 0.42; P < 0.001(27). Finally, in the clinical trial by Duclos et al., In which checklists versus MRC training plus checklists were compared, a decrease in adverse event was shown in the two groups without differences between them, 8.8 to 5.5% (OR 0.57, 95% CI 0.48 to 0.68) versus 7.9 to 5.4% in control (OR 0.64, 0.50 to 0.81) (ROR 0.67 to 1.21)(31); the authors attribute the decrease in the probability of an adverse event to the application of checklists.

In light of this, the checklist is the best strategy to prevent medical error in omitting steps in crisis, which is why the World Health Organization WHO recommends the use of checklists to reduce medical error in surgery. and medication error; and further recommends them as a primary educational component in patient safety competencies.

Research question

In the last semester medical students at the University of Antioquia, does training in nontechnical skills and checklists reduce simulation crisis medical error, compared to training with checklists?

7. Objectives and Hypotheses

Hypothesis

In the last semester of medicine students at the University of Antioquia, training of nontechnical skills and checklists is superior compared to conventional training with checklists to decrease at least 10% omission of steps in crisis management medical in high fidelity simulation.

Primary objective

To determine if the training of non-technical skills and checklists in final semester students of medicine at the University of Antioquia is superior to conventional training with checklists

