The proportion of treatment steps and not the incidence of medical error is taken as the unit of analysis, the reason for this is the high incidence of medical error that can even manifest itself with more than one error due to crisis, therefore, if used the incidence of the event would decrease the sample size.

Based on the study by Arraiga et al., The proportion of missed treatment steps in the expected control group is 26% and we consider a further 10% reduction in the intervention group to be clinically important. A minimum of 10% additional reduction in omitting treatment steps is decided because it is the approximate effect size of the other dimensions of non-technical skills other than resource management, a dimension that includes the use of checklists. It also establishes power of 90% and alpha of 0.05.

The sample calculation is then carried out in the analysis unit omitting treatment steps according to the formula:

$$n = \frac{\left[Z_{*} * \sqrt{2p(1-p)} + Z_{p} * \sqrt{p_{1}(1-p_{1}) + p_{2}(1-p_{2})}\right]^{2}}{(p_{1}-p_{2})}$$

With the statistical program R version 4.0.0 epiR statistical package, with the following code:

> library (epiR)

> epi.propsize (treat = 0.16, control = 0.26, n = NA, power = 0.9, design = 1, sided.test = 2, conf.level = 0.95)

We found a sample size of 492 treatment actions per arm, which corresponds to 984 in total, and with an estimate of student losses of 20%, we found the total of 1,180 treatment actions; Since 21 treatment steps are evaluated in each team, we obtain a total of 56 final semester medical students, 28 in each arm.

15. Recruitment

In order to complete the calculated sample size, the following recruitment strategies will be carried out:

- Explanation of the project at least once per internship cohort with the whole group.
- Request for participation on day 1 of the anesthesiology rotation in boarding school and the care rotation of the critically ill patient.

Table 8. Monthly evaluation of the monitoring status

Recruitment month	one	2	3	4	5	6	7	8
Current current income								
Income to date								
Income goal to date								
Real less projected								
Success ratio								
Projected final income								
Final deficit or excess								

IV Methods: allocation of interventions

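### The 26% control omission rate in section 14 is not supported by the checklist trial it is attributed to for a checklist-trained arm, and whether a 10-point reduction can be reached depends on that rate

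*Combined protocol and SAP*

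**What the plan says.** Section 14 names the checklist simulation trial as its basis and then states: "The proportion of missed treatment steps in the expected control group is 26" per cent. It adds that "we consider a further 10% reduction in the intervention group to be clinically important", and the code uses 0.26 for control and 0.16 for intervention. The 10 points have a separate rationale: "it is the approximate effect size of the other dimensions of non-technical skills other than resource management", with checklist use counted under resource management. The gain is therefore meant to come on top of checklists.

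The checklist trial is described in three places, always by its effect and never by the rate in either arm:

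- Table 4: "Absolute risk reduction: 17% Relative risk of 0.28. IC0.18 to 0.42; P <0.001"
- Section 6a: "the use of checklists reduced the omission of simulation treatment steps with an absolute risk reduction of 17 and relative risk of 0.28"
- Section 6b: "the use of checklists reduces simulation crisis medical error with an absolute risk reduction of 17% and relative risk of 0.28"

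Table 1 gives this trial's comparator as "Control: standard training with checklists". Section 11a describes a 10-hour control programme centred on checklists, which are also used during the simulated crises.

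The alternative hypothesis in section 20a is a control-minus-intervention difference above 10 points. Section 7 words the aim as a reduction of at least 10%.

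**The concern.** The control arm here corresponds to the checklist arm of the cited trial, not to its comparator. A relative risk of 0.28 together with a 17-point reduction points to a checklist-arm rate far below 26%. The only other 26% in the documents is in section 6a, on errors in code situations: "the high incidence reported for this context, which is between 26 and 50" per cent. That range has a different reference and is not specific to checklist users.

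The control rate fixes how much room there is to improve. If it is near the source-implied figure, the 10-point difference cannot occur however good the training is. A null result could then reflect an unreachable target rather than ineffective training, and section 14 gives the reader no warning of this.

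**Working it through.** **Inputs.** Absolute reduction (ARR) 0.17 and relative risk (RR) 0.28, interval 0.18 to 0.42 (Table 4, sections 6a and 6b). Planned rates 0.26 and 0.16 (section 14). Margin of 10 points (section 20a).

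**Can 26% be recovered from the source?** Assume that ARR and RR are crude figures from the same pair of proportions. Then:

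- without checklists: p0 = ARR / (1 − RR) = 0.17 / 0.72 = 23.6%
- with checklists: p1 = RR × p0 = 0.28 × 0.236 = 6.6%

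Rounding of the inputs (ARR 16.5 to 17.5 points, RR 0.275 to 0.285) limits p0 to 0.165 / 0.725 = 22.8% up to 0.175 / 0.715 = 24.5%. On this reading 26% is neither arm's rate.

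**Upper limit of the RR (0.42).** Two calculations are possible, and they rest on different comparators:

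- p0 held at 23.6%: p1 = 0.236 × 0.42 = 9.9%
- ARR held at 17 points: p0 = 0.17 / 0.58 = 29.3% and p1 = 0.293 × 0.42 = 12.3%

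The 12.3% therefore goes with 29.3% without checklists, not with 23.6%.

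**If 26% is instead taken as the rate without checklists.** The checklist rate becomes 0.26 × 0.28 = 7.3%, or 0.26 − 0.17 = 9.0%, or 0.26 × 0.42 = 10.9% at the upper limit. The first two disagree, which again shows that 26% does not fit the crude pair. No route gives 26% with checklists.

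**What a 10-point reduction requires.** Intervention rate = control rate − 10 points; share of omissions removed = 10 / control rate.

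| Control rate | Intervention rate needed | Share removed |
|---|---|---|
| 6.6% | −3.4% | impossible |
| 9.9% | −0.1% | impossible |
| 10% | 0% | 100%; a difference above 10 points is impossible |
| 12.3% | 2.3% | 81% |
| 15% | 5% | 67% |
| 20% | 10% | 50% |
| 26% | 16% | 38% |

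**Power.** With 56 students less 20% losses there are 28 × 0.8 × 21 = 470 steps per arm. Treated as independent and tested two-sided at 0.05 against no difference, 26% versus 16% has about 97% power. But each student contributes 21 steps, and the code sets the design effect to 1. The documents give no intraclass correlation (ICC). At assumed ICCs of 0.02, 0.05 and 0.10 the design effect, 1 + 20 × ICC, is 1.4, 2 and 3, and power falls to about 89%, 76% and 59%. Power by control rate means little without that allowance.

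Separately, the stated 492 steps per arm does not follow from section 14's inputs, which give 347 by the pooled-variance formula. That is a different matter and is not used here.

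**The case against.** The strongest reply is that the cited trial does not determine the rate here. Final-semester students are scored one at a time on Annex 1 steps, with time limits and doses counting towards omission (section 12.1). Section 12.2b foresees that a student may not ask for the list at all. Omissions well above the source's checklist arm are plausible, and at 26% the target is feasible. This stands, but section 14 does not argue it: it cites the trial and offers no student data. Moreover, every participant must score 100% on a crisis-knowledge exam (sections 10a and 11a), so a high rate cannot simply be presumed.

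A second reply is that the arm rates lie in a source not reproduced in the documents, and that ARR and RR may not be a crude pair. That also stands, and makes 6.6% conditional. It does not supply a basis for 26%.

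A third is that section 14 shows its 26% openly in text and code, so any reader knows that the power depends on it. That is fair. What is missing is the limit on feasibility.

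A reader might also infer that the planners took the rate of the source's no-checklist arm by mistake. The documents do not establish this. On the crude reading that arm is at 22.8 to 24.5%. A rate of 26% with a 17-point reduction would need a relative risk of 0.09 / 0.26 = 0.346. Its lying inside the confidence interval does not make it the observed value.

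**Conclusion.** The point holds as one about sourcing and feasibility. For a checklist-trained arm, 26% is not supported by the trial to which it is attributed. The reported effect implies about 7%, and up to about 12% at the upper limit of the relative risk, provided that ARR and RR are crude figures from the same proportions. Where 26% comes from cannot be established from the documents.

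Two stronger conclusions are tempting. One is that the control rate will be about 7%, so that the target is unattainable. The documents do not show this, because population, scoring and checklist use may differ from the source. Impossibility is certain only at a control rate of 10% or below. The other is that the trial lacks power for its stated 10 points because of this rate. That does not follow either: the rate governs whether 10 points can occur.

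**What to change.** In section 14:

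1. Stop attributing 26% to the checklist trial as the rate for a checklist-trained arm. Either support it with relevant data, for example checklist-trained students scored on Annex 1, or restate it as an assumption with its reason. Show the source-implied rate beside it (about 7%, up to about 12%), with the crude-figures condition stated.
2. State that a difference above 10 points cannot be reached at a control rate of 10% or below, and give the share of omissions to be removed at higher rates, as in the table above.
3. If power is shown by control rate, allow for 21 steps clustered within each student over a stated ICC range. Name the null hypothesis, since the 97% above tests against no difference whereas section 20a sets the null at 10 points or less.

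The cost is a few sentences and one small table. Sample size, the 10-point target and the design stay as they are. The downside is a less favourable, conditional planning statement.

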As the teaching-learning relationship is bidirectional, other educational interventions on technical skills related to the scenarios and the resolution of questions and doubts about the technical concepts related to the platform will be allowed for both groups.

No training will be conducted in either group on non-technical skills other than those contained in the training in this protocol.

12. Outcomes

12.1 Primary outcome:

Difference of proportions of omission of steps to treatment by group, the measurement of this outcome will be made by reviewing the recordings of three random medical crises different from those used for training in each group of participants. The evaluation will be done by an independent collaborator blinded to the intervention group and previously trained in the detection of errors by one of the authors. Failure to apply the specific actions defined in each pathology, chosen by the authors according to Annex 1, will be considered as omission of the treatment step, this includes the maximum time determined for each action, the choice of appropriate medications with their respective doses, among others. Each evaluation is independent, each crisis will be evaluated in seven steps,

12.2 Secondary outcomes:

12.2a 1Difference of crisis resolution time averages in seconds between both groups, measured in the recording, taking as the beginning of the crisis the moment of calling the treatment team and the end when all the effective treatment of each crisis is completed, according to the treatment steps described in Annex 1. In the event that the treatment steps are not fully completed, the time will be measured until the end of the simulation.

12.2b Difference of time averages in detection and discrimination of the crisis in seconds between both groups, taking as the beginning of the crisis the moment of calling the treatment team and the end the moment of explicitly requesting the specific checklist for the crisis or verbalize the diagnosis of the code situation. If the specific list is not requested or the diagnosis is not verbalized, the time until the end of the simulation will be counted.

12.2c Mean difference between the global non-technical skills score measured with the Ottawa global scale based on video recording by an independent evaluator.

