The participation, retention and follow-up of the study will be voluntary, based on the explanation of the potential benefits in the participation of the study, such as training in high-fidelity simulation of both interventions, no financial remuneration will be used as a retention strategy.

Since a minimum of three sessions participation on different days is required for high-fidelity simulation training and outcome measurement, a possible participant loss of 20% is considered, which was included in the sample size calculation.

The participant can withdraw from the study at any time they wish, even after randomization, this will be clarified from the beginning of the intervention and follow-up period, in addition it will not have repercussions on any qualification in any of the internship courses to be attended by the competitor.

It will be carried out independently of the possible withdrawals from the study, analysis by intention to treat.

19. Data handling:

After completing the manual forms in their entirety, they will be subjected to quality control during the days of administration of the interventions, avoiding loss of data from the start of the study. After that, the central office of the present investigation located in the Faculty of Medicine of the University of Antioquia will be taken in an opaque and sealed envelope, where an administrative assistant with experience in electronic data management and investigation will enter the information from the formats. manuals to an electronic database that will have two backup copies and to which said assistant will only have access during data collection. Subsequently, they will be presented blinded to the researcher who will carry out the statistical analyzes described in the analysis plan.

20 a. Analysis methods for primary and secondary outcomes.

The baseline characteristics of the participants in both groups will be summarized with measures of frequency and proportions for the qualitative variables. In the case of quantitative variables, measures of central tendency and dispersion, mean and standard deviation or median and interquartile range will be used after performing the Shapiro Wilk normality test.

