The analysis of each variable is explained in Table 9, prior to the use of parametric tests, the necessary assumptions will be verified including probability distribution tests, independence of the data and equality of variances according to the case. For the ratio of proportions and mean differences of the groups, in case of non-compliance, non-parametric statistical inference will be made.

To compare the intervention arm: training with non-technical skills and checklists with the control group: training with checklists, the proportion of omission of treatment steps per group will be used as the primary outcome variable.

Alternate hypothesis: the difference in the proportion of omission of treatment steps between the control and intervention group is greater than 10%.

Null hypothesis: the difference in the proportion of omission of treatment steps between the control and intervention group is 10% or less.

Table 9 analysis plan by variable

Outcome	Outcome	Statistical	Estimator	Analysis
	measure	hypothesis		method
Primary outcome: Medical error	Ratioofomissionoftreatmentstepsto totalstepsgroup.	Ha: Pcontrol - P intervention> 10% HO: Pcontrol - Intervention = 10%	Difference in proportions (95% CI)	Chi square test
Overall score on non-technical skills scale	Average Interval per group between 1 to 45	He has: µintervention>µcontrol Ho: µintervention≤ µcontrol	Mean difference (95% Cl)	T Student test.
Ottawa Leadership on Scale	Average Interval per group between 1 and 7	He has: µintervention>µcontrol Ho: µintervention≤ µcontrol	Mean difference (95% CI)	T Student test.
Ottawa scale problem solving	AverageIntervalpergroupbetween 1 and 7	AverageIntervalper groupbetween1 and 7	Mean difference (95% CI)	T Student test.
Situational awareness on the Ottawa scale	AverageIntervalpergroupbetween 1 and 7	Hehas:µintervention>µcontrolHo:µintervention≤µcontrol	Mean difference (95% CI)	T Student test.
Utilization of Ottawa scale resources	Average Interval per group between 1 and 7	He has: µintervention>µcontrol Ho: µintervention≤ µcontrol	Mean difference (95% CI)	T Student test.
Ottawa Scale Communication	Average Interval per group between 1 and 7	He has: µintervention>µcontrol Ho: µintervention≤ µcontrol	Mean difference (95% CI)	T Student test.
Crisis resolution time	Average time in minutes per group	He has: µintervention< µcontrol Ho: µintervention≥ µcontrol	Mean difference (95% CI)	T Student test.

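### The 492 steps per arm do not follow from the stated inputs, which give 347, and the 20% loss is added by multiplying by 1.2 instead of dividing by 0.8

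*Combined protocol and SAP*

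**What the plan says.** Section 14 takes the treatment step as the unit of analysis. It sets the control proportion ("The proportion of missed treatment steps in the expected control group is 26"%) and an absolute reduction of 10 points, and adds: "It also establishes power of 90% and alpha of 0.05". The printed R call has 0.16 and 0.26 as the two proportions and ends with "power = 0.9, design = 1, sided.test = 2, conf.level = 0.95". Section 16a gives 1:1 allocation.

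The result is reported as "We found a sample size of 492 treatment actions per arm, which corresponds to 984 in total". The section continues "with an estimate of student losses of 20%, we found the total of 1,180 treatment actions", then divides by 21 steps per team to reach 56 students, 28 per arm. The 21 comes from three recorded crises per participant (section 11a, recording for measurement of outcomes), and section 12.1 says "each crisis will be evaluated in seven steps". Section 18b repeats that "a possible participant loss of 20% is considered, which was included in the sample size calculation".

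**The concern.** Every input to the calculation is printed, and text and code agree on alpha and power, so the result should be reproducible. It is not. The figure carried forward is much larger than the inputs require, and the loss step uses the wrong operation, so the section misses even its own declared requirement.

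Two things are at stake. First, the 90% power is not supported by the calculation shown. On the plan's own assumptions 56 students give more than 90%; once steps within a student are correlated they may give much less. Second, a reader who recomputes from the stated inputs will find 347 and may take the difference as room to recruit fewer students. The significance level of the primary test is not affected by this point.

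**Working it through.** **Inputs** (section 14 unless noted): p₁ = 0.26, p₂ = 0.16, mean p = 0.21; two-sided alpha 0.05 (z = 1.960); power 0.90 (z = 1.2816); design effect 1; 1:1 allocation (section 16a); loss 20% (sections 14 and 18b); 21 steps per student.

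**Attempt to reproduce 492.** Pooled formula with squared denominator:

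n = [1.960·√(2·0.21·0.79) + 1.2816·√(0.16·0.84 + 0.26·0.74)]² / 0.10²
= [1.1290 + 0.7326]² / 0.01 = 3.4655 / 0.01 = 346.6, i.e. **347 per arm, 694 in total**.

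The excess is 492 − 347 = 145 steps per arm (42%). Other versions at the same alpha and power:

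| Version | n per arm |
|---|---|
| Pooled | 347 |
| Unpooled variance | 344 |
| Arcsine | 345 |
| Continuity-corrected | 367 |
| Section 14 | 492 |

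Two-sided alpha 0.01 gives 491.2, which rounds up to 492. A continuity-corrected calculation at alpha 0.0125 gives 491.3, which also does. The documents mention neither, so the origin of 492 cannot be inferred. The calculation above is the formula; the R call itself was not run.

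**The rest of the chain does follow from 492.** 2 × 492 = 984; 984 × 1.2 = 1,180.8 (printed as 1,180); 1,180/21 = 56.2 (printed as 56). So 492 is the figure the authors actually used, not a misprint.

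**Loss step.** To keep 984 after losing 20%: 984/0.8 = 1,230 steps, and 1,230/21 = 58.6 students. With 56 students: 56 × 21 = 1,176 steps, and 1,176 × 0.8 = 940.8 remain. That is 43 below 984, but above 694.

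**What 56 students deliver.** 940.8/2 = 470.4 steps per arm. With independent steps and a null of no difference:

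z = [0.10·√470.4 − 1.1290] / 0.5717 = 1.819, so power is **96.6%**. For comparison, 347 per arm gives 90.0% and 492 gives 97.2%.

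**Sensitivity to correlation within a student.** The documents give no intraclass correlation (ICC) for omissions; the ICCs in Table 5 are rater reliability for the Ottawa scale. The values below are assumptions. Design effect DE = 1 + (21 − 1)·ICC; power is evaluated at 470.4/DE steps per arm; students needed = 2·⌈346.6·DE/(21·0.8)⌉.

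| Assumed ICC | DE | Power with 56 students, 20% loss | Students for 90% power |
|---|---|---|---|
| 0.01 | 1.20 | 93% | 50 |
| 0.018 | 1.36 | 90% | 58 |
| 0.02 | 1.40 | 89% | 58 |
| 0.03 | 1.60 | 85% | 68 |
| 0.05 | 2.00 | 76% | 84 |
| 0.10 | 3.00 | 59% | 124 |

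Power falls below 80% at an ICC of about 0.041.

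**The case against.** The strongest reply is that nothing is harmed. Under the plan's own design effect of 1, 56 students less 20% leave about 470 steps per arm, well above 347. The loss slip has no consequence once 984 is replaced by 694, because 941 exceeds 694. Every power below 90% comes from correlations that the reviewer assumes and from a simple design effect that ignores the nesting of seven steps within each of three crises. Clustering, on this view, is a separate question of design and analysis.

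Much of this stands. The first error is conservative on the plan's terms, the loss slip is secondary, and the ICC table is context, not a measured result. At an assumed ICC near 0.018 the 56 students would in fact give about 90%, so the claim can only be that the printed calculation does not support 90%.

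It does not remove the point. Students are randomised and each contributes 21 steps, so independence is the assumption least likely to hold, and the apparent surplus offsets only a small correlation. Planned intention-to-treat analysis and multiple imputation (sections 18b and 20c) do not restore the information lost with students who drop out. The justification for the primary sample size still cannot be reproduced.

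**Conclusion.** The concern holds. The stated inputs require 347 steps per arm (694 in total), not 492 (984), and the 20% loss is applied with the wrong operation. The trial is not underpowered on its own terms: expected power is 96.6% if steps within a student are independent. Without a stated ICC the real power is undocumented; over assumed values of 0.01 to 0.10 it runs from 93% to 59%.

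All these powers are for a null of no difference. Section 20a instead states: "Null hypothesis: the difference in the proportion of omission of treatment steps between the control and intervention group is 10% or less". That null contains the assumed 10-point effect, so none of the powers above apply to it. The conflict is a separate matter and must be reconciled in its own right.

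**What to change.** Restate section 14 along these lines:

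> For omission proportions of 26% and 16%, two-sided alpha 0.05, 90% power and independent steps, 347 steps per arm (694 in total) are required before losses. Losses of 20% are allowed for by dividing by 0.80. The planned 56 students are expected to provide about 470 evaluable steps per arm after losses, giving 96.6% power if steps within a student are independent. Power under within-student correlation is 93% at an ICC of 0.01, 90% at 0.018, 85% at 0.03, 76% at 0.05 and 59% at 0.10.

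The team should add which ICC it assumes and why, and drop the unqualified 90%. If 492 came from a different alpha or method, say so and make text and code agree. Check the denominator of the printed formula against the source file; the missing square may only be lost in conversion.

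The sample should not be cut to 42 students (694/0.8/21 = 41.3) on the strength of 347.

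The arithmetic correction is a text change to one section and neither raises nor lowers recruitment. Choosing an ICC is a real decision: by the table above, an assumed ICC of 0.05 or 0.10 would put the target for 90% power at 84 or 124 students. Whether 56 is enough also depends on which null is tested.
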